- (10) Have any pending legal action that could prohibit continued participation.
- (11) Be expecting to leave the clinic=s geographic area prior to study completion.

PROCEDURES:

Patient Assignment and Length of Study: Eligible patients will be given an explanation of the study. Study participation will be 9 to 12 weeks for patients who successfully achieve detoxification and up to 12 months for patients requiring longer buprenorphine treatment.

This will be an open-label study with no random assignment or stratification. Each principal investigator (PI) may recruit up to 5-10 site physicians working in a variety of care delivery settings. Physician eligibility will be determined by the PIs and the sponsor (National Institute on Drug Abuse). Each site physician may admit up to 10-20 patients per site (90-110 patients per state). All patients will sign an informed consent approved by national and local Institutional Review Boards. Patients under 18 years of age must also obtain concurrent consent from a parent or guardian, as applicable. Prior to starting the study and after signing the informed consent, patients will receive the following:

A general medical and psychiatric evaluation, including a history of drug use and assessment of HIV risk, any medical or psychiatric illness requiring ongoing treatment, and any concomitant medications received either over the counter or under the prescription of a physician. Off-site HIV testing and HIV counseling will be encouraged.

A physical examination (to be repeated at the end of the study to the extent possible) to include vital signs, ECG for all patients over 40 and for patients under 40 with a history of cardiovascular disease, routine laboratory chemistry panel, urinalysis, and urine screen for drugs of abuse. Urinalyses will be performed weekly throughout the first 9 weeks of the study and periodically thereafter (for an anticipated maximum of 21 urine tests per 12 month treatment*) to test for drugs of

abuse. Females will also undergo pregnancy testing at baseline and monthly during their study participation.

Treatment Schedule: The following treatment schedule will apply according to the specific treatment setting assignment:

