Week 1: On the first day of treatment, patients will see the site physician and receive a 2, 4 or 8 mg dose (expressed as amount of buprenorphine) of the buprenorphine/naloxone combination tablet to be taken sublingually. Patients may receive an additional buprenorphine/naloxone dose of up to a maximum of 8 mg at the site physician=s discretion. Patients should be prescribed enough medication to continue dosing until the next office visit. Patients will make contact with the site physician on the following day and be seen by the physician at least one more time during the first study week for follow-up evaluation to include drug use, signs and symptoms of opiate withdrawal or over medication, and any adverse medication effects. At this time, dosage may be adjusted, by 8 mg/day increments, up to a daily maximum of 24 mg buprenorphine (24 mg will be the maximum dose used throughout the study.)

Weeks 2-6: Patients will see the site physician once weekly for evaluation of treatment progress and medication effects and side effects. A urine sample will be obtained at each visit to screen for drugs of abuse. Additional visits may be scheduled as medically indicated. During this treatment period, a decision will be made as to whether the patient can be detoxified or should continue in buprenorphine/naloxone treatment.

After Week 6: Patients expected to be successfully detoxified will have their buprenorphine/naloxone dose tapered according to the physician=s discretion from weeks 7 to 9. If the taper is unsuccessful, patients may remain on buprenorphine/naloxone. Patients needing further buprenorphine treatment will be continued on medication with doses adjustable to 24 mg/day maximum. These patients will be seen by the site physician weekly for the next 3-6 weeks for review of their treatment progress and to explore other treatment options, including further continuation of buprenorphine treatment.

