Detoxification vs Maintenance: The decision to detoxify will be based on patient performance. As a minimum criterion for buprenorphine tapering, at least half of the urine samples obtained between weeks 3 and 6 must have been negative for opiates including the last sample obtained in week 6. If it is decided that detoxification should be attempted, the buprenorphine dose will be tapered over the next 3 weeks until, by week 9, Azero@ mg dose is achieved. The rate of taper will be individually determined. If detoxification appears impossible due to inability to achieve minimum criteria,

buprenorphine treatment will be continued for up to 52 total weeks. During this extended treatment period other treatment options will be explored or subsequent detoxification may be attempted.

Missed visits: Patients should be encouraged to keep their scheduled appointments. After two missed visits, patients should be considered for reinduction and dose scale up. Alternatively, patients may be re-evaluated for other types of therapy if compliance is poor.

Urine Screening for Drugs of Abuse: Urine samples will be obtained weekly for the first 9 weeks of treatment and assayed for the presence of opiates, benzoylecgonine, benzodiazepines, and amphetamines. Thereafter, an additional 12 urines* may be obtained if the patient stays in for the full year of treatment. Clinical decisions on extending the length of prescriptions for buprenorphine can be made, in part, on the urine results.

Psychosocial Treatment: In addition to the site physician=s visits, patients can receive psychosocial treatment from any of the following sources: an on-site medical assistant (trained to administer relapse prevention counseling), a drug counselor (on-site or off-site), or Narcotics Anonymous. For patients who will undergo detoxification, the psychosocial treatment will be extended to week nine and, thereafter, patients will be encouraged to enroll in aftercare self-help groups. Patients who require further treatment with buprenorphine will continue to participate in relapse-prevention programs at reduced frequency of visits. Patients receiving long-term buprenorphine/naloxone

treatment may receive up to 26 counseling sessions in the first year. In addition to the psychosocial treatment provided as part of this protocol, patients will be encouraged to attend other self-help support groups in the community (e.g., AA, NA).

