Post-Treatment Follow-Up: Patients will be contacted for a 30-day follow-up assessment of their post-treatment status. This will consist of self-report of whether the patient is currently using opiates

or other drugs illicitly and/or currently receiving substance abuse treatment (drug or alcohol). The patient will also be asked if they would take the study medication again if it were generally available for opiate dependence treatment. If the patient is deceased, the date and cause of death will be obtained and site staff will verify the information. This information will be captured on Form 12.

Pregnancy: Women of childbearing potential must have pregnancy tests performed monthly using an FDA approved device or method. Women becoming pregnant during the study will be referred to a methodone program.

Study Termination: Patients may be terminated from the study if the site physician determines that it is in the patient=s best interest (ex. safety concerns, etc.). A patient may also be removed for continued failure to keep appointments and for diverting or failure to handle medications

^{*}Additional tests may be performed if a therapeutic need arises.

responsibly. Women who become pregnant during the course of the study will be referred for methadone treatment. Patients who drop out or are terminated from the study will not be readmitted.

MEDICATION

Medication will be supplied free of charge from Reckitt and Colman through NIDA. Medication will be tamper-proof and labeled with the following warning:

ACaution: New Drug - Limited by Federal (or United States) Law to Investigational Use. @

The 4:1 combination tablet will be supplied in the 2mg/.5mg and 8mg/2mg buprenorphine/naloxone strengths. Medication will be supplied in blister packs as a one-week supply, and labeled as follows:

ABuprenorphine/naloxone combination tablets (2mg/.5mg and 8mg/2mg).

In case of emergency, please call:

(telephone number to be determined)@

Medication will be stored in a secure, limited-access location under the conditions specified by the label.

Medication Dispensing: The site physician will prescribe buprenorphine/naloxone for pick up at a specified local pharmacy. A two to four-week supply of medication will be the maximum dispensed

or prescribed at any time during the course of the study. Take-home medication will be provided according to the following schedule:

Week 1: Enough medication will be dispensed to last between visits by the site physician.

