Weeks 2-6: A one-week supply of medication will be dispensed or prescribed.

Weeks 6-12: A one-week supply of either tapering (weeks 6-9) or fixed dose medication will be dispensed or prescribed.

Beyond Week 12: Take-home doses may be dispensed or prescribed at the discretion of the physician, not to exceed a two-week supply for weeks 13-26 and not to exceed a four-week supply for weeks 27-52. Patients should be considered for a dose tapering regimen or transfer to a methadone program during the last four weeks of the study.

Other Medical Treatment and Concomitant Medications: Patients may receive other treatment and concomitant medication provided they do not interfere with buprenorphine treatment. If such treatment is provided by other than the site physician, both physicians must be made aware of, and concur with the other treatment.

Medication Replacement: There will be no replacement of any prescribed or dispensed medications.

Drug Accountability: The site physician and the pharmacy will maintain an accurate and current accounting of all dispensed and returned medication. Such records will be made available for verification by the study project monitor. Returned medications will be accurately labeled and kept separately until the end of the study. The medication will then be returned to the Cooperative Studies Program Clinical Research Pharmacy Coordinating Center (CSPCRPCC) or otherwise properly disposed of. Returned medication will not be re-used.

Medication Compliance: At each visit, patients will be required to bring all unused medications to the site physician=s office for accounting. The amount of buprenorphine returned and any discrepancy in medication counts will be recorded. To verify medication compliance, there will be one random call back during the first 9 study weeks and two during the remainder of the study. The random (or unannounced) medication callbacks will require contacting the patient and asking them to come to the site physician=s office and have all of the medication in their possession counted. The amount of medication they bring should show that they are taking the medication as prescribed.

MEASURES

Clinical Rating Instruments

The measures for this study are the Risk Assessment Battery (RAB), the Addiction Severity Index (ASI), the Opiate Symptom Checklist, the physician=s assessment of overall condition, the DSM-IV checklist for dependence.

DSM-IV Checklist for Substance Dependence - Form 06

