The Clinical Global Impression Scale - Self is a patient-rated instrument of severity and global impression of change from the patient=s own perspective. The clinician will record the patient=s impression of their improvement on a 5-point scale from Amuch worse@ to Amuch improved.@ The severity item will be rated prior to enrollment and the global impression of change will be rated at each office visit throughout the study, including the follow-up visits. It should take less than 5 minutes to complete.

Physician=s Survey - Form 14

The Physician=s Survey is a questionnaire that each site physician will be asked to complete at the end of the study. It will record such information as usual prescribing patterns, adjustments required for

integration into their treatment setting, and ease and effectiveness of administration to a younger population.

Patient=s Survey - Form 15

The Patient=s Survey is a questionnaire that each patient will be asked to complete at the end of the study. It will record such information as the patient=s acceptability of office-based treatment, whether they felt that the office-based paradigm made it easier to be compliant, what their preferences would be and what adjustments, if any, that they found necessary to make.

Efficacy Evaluations

The outcome measures will include opiate use as determined by the urine drug screens, the clinical ratings from the opiate symptom checklist, the clinical global impression scales, and patient retention in the study. The primary focus will be on patient retention in the study and opiate use as determined by the urine drug screens.

Additional secondary outcome measures will include scores on the ASI, RAB, and opiate symptom checklist.

Safety Evaluations

Safety assessments will include a physical examination during the screening phase and upon termination from the study, laboratory tests taken during the screening phase and upon termination from the study, vital signs and urine drug screens obtained weekly, weekly evaluations by the site physician, and opportunities to report adverse events each week. In addition, monthly pregnancy tests will be performed on women of child-bearing potential.

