Patients will be interviewed and monitored weekly for adverse experiences throughout the treatment period under the direct close supervision of the investigator or designated staff. All adverse experiences, either observed by the site physician or one of his/her professional colleagues, or reported by the patient spontaneously or in response to a direct question will be noted in the adverse events section of the patients Case Report Form.

The site physician or designated staff will evaluate the intensity, seriousness, and causal relationship to the study medication of all adverse experiences whether or not thought to be drug related. Any adverse experience will be recorded and listed on the CRF. The IRB and the sponsor, NIDA, will be informed by telephone within 24 hours by the investigating institute of any serious adverse experiences. A written report to NIDA will follow within three days. All serious adverse events will be reported whether or not considered drug-related.

Definitions of serious, unexpected or life-threatening experiences are summarized below.

Serious Adverse Experiences: Any adverse experience that is fatal or life-threatening, results in persistent or significant disability or incapacity, requires inpatient hospitalization or prolongation of hospitalization, requires intervention to prevent permanent impairment or damage, or is a congenital anomaly/birth defect.

Unexpected Adverse Experiences: Any experience that is not identified in nature or severity in the current literature (e.g., Investigator=s Brochure, Buprenex labeling).

Life-Threatening Experiences: Patient is, in the view of the site physician, at IMMEDIATE risk of death from the reaction as it actually occurred. This definition does not include reactions that might be fatal if they were to occur in a more severe form.

In addition, any overdose should be reported to NIDA within 24 hours.

A complete list of definitions for the terms used to describe clinical and laboratory adverse experiences is given in Appendix I. The regulatory reporting time frames are also given in this appendix.

In the event of an adverse event felt to reflect drug-related toxicity, appropriate evaluation and management will be undertaken and may include, in addition to medical management, a reduction in

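### Safety Evaluations sets urine screens as weekly with no end week, against a schedule that is weekly only to week 9, and no visit or vital-sign interval is fixed after week 9-12

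*Protocol*

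**What the plan says.** **Safety section.** Protocol, Safety Evaluations, lists "vital signs and urine drug screens obtained weekly, weekly evaluations by the site physician, and opportunities to report adverse events each week". No end week and no reference to the visit schedule is attached. The same section then says: "Patients will be interviewed and monitored weekly for adverse experiences throughout the treatment period".

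**Duration.** Procedures, Patient Assignment and Length of Study, allows 9 to 12 weeks for patients who detoxify and "up to 12 months for patients requiring longer buprenorphine treatment".

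**Urines.** Procedures plans weekly tests for the first 9 weeks and periodic tests after that, with an "anticipated maximum of 21 urine tests per 12 month treatment". Urine Screening for Drugs of Abuse repeats the nine weekly samples and adds 12 that "may be obtained if the patient stays in for the full year of treatment". A footnote allows extra tests for therapeutic need.

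**Physician visits.** Treatment Schedule sets weekly visits in weeks 2-6. For patients who continue, After Week 6 says: "These patients will be seen by the site physician weekly for the next 3-6 weeks". No interval is given beyond that.

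**Supply.** Medication Dispensing says: "The site physician will prescribe buprenorphine/naloxone for pick up at a specified local pharmacy". Beyond week 12 the amount is at the physician's discretion, "not to exceed a two-week supply for weeks 13-26 and not to exceed a four-week supply for weeks 27-52". Neither statement ties a renewal to a visit.

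**Adverse-event tables.** Analyses of Safety leaves out adverse experiences that occurred during screening only if they also ended before enrollment. It summarises adverse events, vital signs and laboratory tests overall, by site and by treatment setting.

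**The concern.** A site treating a patient for a year finds two urine frequencies in one document and cannot meet both. Opiate use by urine screen shares the primary focus with retention, so the intended schedule should not be in doubt.

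Vital signs are in a different position. Safety Evaluations is the only place that gives them a frequency during treatment; Procedures has them only within the physical examination, at entry and at the end of the study. If the weekly statement is taken to end with the scheduled weekly visits, no vital-sign frequency is left for later weeks. If it runs to week 52, it asks for weekly visits that the Treatment Schedule does not provide. The rules on missed visits and on removal for failing to keep appointments also presuppose a known visit interval.

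The study is meant to establish safety in office-based care and to support labeling. Where each physician sets the frequency of vital signs after week 12, differences between settings in the vital-sign summaries could partly reflect how often patients were measured.

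The adverse-event rule is a separate matter. An event that began before any drug and is still present at enrollment enters the tables alongside events that arose on treatment.

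**Working it through.** **1. The plan's own urine figure.** Inputs: 9 weekly urines and 12 additional urines (Procedures; Urine Screening for Drugs of Abuse). 9 + 12 = 21, which matches the stated maximum.

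**2. The weekly statement over a full year.** Weekly for 52 weeks gives 52 urines. 52 - 21 = 31 more than planned; 21/52 = 40%. In weeks 10-52 there are 52 - 9 = 43 weeks and up to 12 urines: 12/43 = 28% of weekly, on average one every 43/12 = 3.6 weeks. The exception for therapeutic need does not turn this into weekly testing.

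**3. Weekly physician visits.** Last scheduled weekly visit: week 6 + 3 = 9 to week 6 + 6 = 12. Weeks with no stated interval: 52 - 12 = 40 to 52 - 9 = 43, that is 40/52 = 77% to 43/52 = 83% of the year.

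**4. What the supply ceilings imply.** Weeks 13-26: 14/2 = 7 renewals. Weeks 27-52: 26/4 = 6.5, so 7. Together at least 14 renewals in weeks 13-52, against 40 weekly evaluations (14/40 = 35%). These are renewals; the Protocol does not make them visits.

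**5. How many patients this could concern.** Efficacy Analyses cites earlier studies with 51% retention at 16 weeks and 24% to about 30% at 52 weeks. The 24% follows from 0.51 x 0.82 x 0.57 = 0.238. Assume the same retention among 600 patients here. The Protocol gives no detoxification share, so d is an assumed share of these patients who instead leave after detoxification, and the counts are multiplied by (1 - d).

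| d | In treatment at week 16 | In treatment at week 52 |
|---|---|---|
| 0 | 600 x 0.51 = 306 | 600 x 0.24 = 144 to 600 x 0.30 = 180 |
| 0.25 | 230 | 108-135 |
| 0.50 | 153 | 72-90 |
| 0.75 | 77 | 36-45 |

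These are patients still in treatment. They do not measure any bias.

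**6. Adverse-event rule.** An event with onset in screening that ends before enrollment is excluded. An event with onset in screening that is ongoing at enrollment is not excluded, although it preceded the drug. The number of such events cannot be derived from the Protocol.

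**The case against.** The strongest reply is that Safety Evaluations is a one-sentence list of assessment types and that Procedures is the operative schedule. On that view a site would follow the specific urine plan, which is stated twice and adds up, and would hardly be misled. This is fair as to practical harm, but the urine sentence is still wrong as written.

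For physician visits and vital signs the reply goes further. A reader might infer that the Treatment Schedule contradicts the weekly statement here too. It does not: after week 9-12 it is silent and sets no lower frequency, so a site that kept weekly evaluations would satisfy both sections. What stands is that no interval is stated where one is needed.

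A reader might also infer that adverse-event ascertainment thins out after week 12 and varies by setting. The Protocol does not support this. It fixes weekly inquiry for the whole treatment period, under the investigator or designated staff, and staff can do this without an office visit.

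Nor do visits or contacts cease. Ratings are due at every office visit throughout the study, and there are monthly pregnancy tests, up to two later medication callbacks and up to 26 counseling sessions. None of these sets a physician-visit or vital-sign interval. Some freedom is also deliberate, since one aim is to document how physicians prefer to prescribe. A minimum interval leaves most of that freedom in place.

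On the adverse-event tables, one can say that an on-treatment definition is commonly left to the SAP. Here, though, the Protocol states a rule of its own, and that rule can be corrected where it stands.

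**Conclusion.** The point holds in a limited form. The urine frequency is a direct contradiction: 21 anticipated at most against 52 if weekly for a full year. For vital signs and physician evaluation the defect is a missing interval covering 40 to 43 of 52 weeks.

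It concerns only patients treated beyond week 9-12; those who detoxify and leave by then are largely covered by the weekly schedule. Under the retention and detoxification assumptions above, 77 to 306 of 600 patients would still be in treatment at week 16 and 36 to 180 at week 52. No sample size or precision depends on this, the safety summaries are descriptive, and the effect on vital-sign summaries by setting cannot be sized. The adverse-event counting rule is a separate, smaller defect, also of unknown size.

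**What to change.** - **Safety Evaluations, urines:** weekly to week 9, then up to 12 over weeks 10-52.
- **Safety Evaluations, vital signs and physician evaluation:** weekly to week 12, then at least at each prescription renewal, so at most 2 weeks apart in weeks 13-26 and at most 4 weeks apart in weeks 27-52. Give After Week 6 the same week-12 limit so that the two sections agree.
- **Medication Dispensing:** add that a renewal requires a visit.
- **Weekly adverse-event inquiry:** keep it unchanged throughout treatment and say that staff make the contact between visits. Moving it to the renewal interval would weaken safety monitoring.
- **Analyses of Safety:** count as on-treatment only adverse events that start or worsen after the first dose, and list earlier events separately.

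The cost is a few wording changes and a small visit burden. A full-year patient at the supply ceilings would have at least 14 visits in weeks 13-52, fewer than the 40 that the weekly statement implies if read to week 52. Where a physician would have stopped weekly visits at week 9, up to 12 - 9 = 3 more are added. Visit frequency may still differ between settings, because the ceilings are maxima, but there would be a common minimum.

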study drug dose, temporary cessation of study drug, or early termination of the trial. Any patient who receives at least one dose of study medication will be included in the evaluation for safety. Patients who do not receive at least one dose of study medication will be listed separately.

Compliance

Compliance to dosing will be measured via pill counts at each visit and by random medication callbacks. One callback will occur during the first 9 weeks of the study; and up to two more will occur during the remainder of the study.

Data Analysis

Power and Sample Size Considerations

Retention rate is one of the primary outcome measures and is a proportion. Many of the descriptions of the patients= use as determined by opiate positive urines may also be a proportion (e.g., percentage of subjects who have 6 consecutive clean urines). The maximum variability for a proportion occurs when the proportion equals one-half, thus any sample size estimate obtained for this proportion would be conservative in that it will require more subjects than actually needed. To compute a 95% confidence interval for the observed proportion, with precision of $\pm 5\%$, a sample size of approximately 400 is needed when the expected proportion is 0.5.

Since the dropout rate is expected to be between 70 and 80%, the total number of patients that need to be enrolled is between 500 and 575. This number has been rounded to 600 to permit each of the primary VA Medical Centers (across 6 states) to enroll about 100 subjects. Each site physician will be allowed to enroll between 10 and 20 subjects so that they gain sufficient experience to permit results to be generalized.

Demography and Baseline Outcome Analyses

The number of patients enrolled in the study will be summarized overall, by site and by treatment setting. For patients who are screened but not enrolled, a distribution of the reasons for discontinuation will be provided.

Demographic, as well as other pretreatment characteristics and baseline parameters, will be summarized overall, by site and by treatment setting.

Efficacy Analyses

Although the study design does not permit an unconfounded assessment of treatment efficacy, treatment improvement, or lack thereof, will be documented.

Patient retention rates will be the primary outcome measure and will be summarized using descriptive statistics, overall, by site and by treatment setting. The NIDA-VACSP Multicenter Buprenorphine

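### The claim that about 400 patients give ±5 points is conservative only in the choice of p: it treats patients as independent although each site physician contributes 10 to 20 of them

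*Protocol*

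**What the plan says.** Under Data Analysis, Power and Sample Size Considerations, the protocol sizes the study by precision for a proportion. Retention is named, and urine-based proportions are mentioned alongside it. The target is introduced with "To compute a 95% confidence interval for the observed proportion", the half-width is 5 percentage points, and the result is that "a sample size of approximately 400 is needed when the expected proportion is 0.5". Because variance peaks at one half, the section adds that "any sample size estimate obtained for this proportion would be conservative in that it will require more subjects than actually needed". It then inflates for dropout, says that "the total number of patients that need to be enrolled is between 500 and 575", and rounds to 600.

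The same section states that "Each site physician will be allowed to enroll between 10 and 20 subjects", so that each physician gains enough experience for the results to generalise. Procedures, Patient Assignment and Length of Study, agrees: "Each site physician may admit up to 10-20 patients per site (90-110 patients per state". At 10 to 20 patients each, 600 patients imply about 30 to 60 physicians.

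Physicians have a say in matters that bear on the outcomes. Under Treatment Schedule, After Week 6, patients expected to detoxify have their "dose tapered according to the physician=s discretion from weeks 7 to 9". Study Termination lets the site physician end a patient's participation. Medication Dispensing leaves take-home supply after week 12 to the physician, within limits. One of the Specific Aims is to record how physicians' prescribing patterns look in practice.

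No design effect, ICC or other allowance for grouping by physician appears in the protocol.

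**The concern.** A binomial interval is valid when patients are independent. Patients of one physician share that physician's habits on taper, termination and supply, as well as the type of practice and its local population. If this makes their outcomes more alike, 600 patients carry the information of fewer than 600, and the half-width for a given n is wider than the formula says.

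The section also describes the estimate as needing more subjects than is really necessary. That follows from taking p = 0.5, but it says nothing about correlation, which acts in the opposite direction. A reader would take 400 as a safe figure and 600 as generous, when part of the margin may already be spent. The study is meant to support labelling and guidance for office-based treatment, so the precision attached to its main proportions should be stated correctly.

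**Working it through.** **Inputs from the protocol.** 95% interval, half-width d = 0.05, p = 0.5, n about 400, enrolment 600, m = 10 to 20 patients per physician (Power and Sample Size Considerations). Earlier 52-week retention of 24% and about 30% of all patients enrolled (Efficacy Analyses).

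**Assumption.** ICC 0.01 to 0.10. The documents give no value, so the range is illustrative. Clusters are taken as equal in size.

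**Step 1: reproduce the plan's figure.** n = z²p(1−p)/d².
- z = 1.96: 3.8416 × 0.25 / 0.0025 = 384.2, so 385.
- z rounded to 2: 4 × 0.25 / 0.0025 = 400.
- With a continuity correction: 404.

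The enrolment range follows as 400/0.8 = 500 and 400/0.7 = 571. (This uses the 70 to 80% as the share kept, although the text calls it dropout. That is a separate matter.) Every version that gives the stated figure has a design effect of 1.

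**Step 2: allow for clustering.** DE = 1 + (m − 1) × ICC; half-width = 1.96 × √(p(1−p) × DE / n). Half-widths in percentage points:

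| ICC | m | DE | n=400, p=0.5 | n=600, p=0.5 | n=600, p=0.30 | n=600, p=0.24 |
|---|---|---|---|---|---|---|
| 0.01 | 10 | 1.09 | 5.12 | 4.18 | 3.83 | 3.57 |
| 0.01 | 20 | 1.19 | 5.35 | 4.36 | 4.00 | 3.73 |
| 0.03 | 10 | 1.27 | 5.52 | 4.51 | 4.13 | 3.85 |
| 0.03 | 20 | 1.57 | 6.14 | 5.01 | 4.59 | 4.28 |
| 0.05 | 10 | 1.45 | 5.90 | 4.82 | 4.42 | 4.11 |
| 0.05 | 20 | 1.95 | 6.84 | 5.59 | 5.12 | 4.77 |
| 0.10 | 10 | 1.90 | 6.75 | 5.51 | 5.05 | 4.71 |
| 0.10 | 20 | 2.90 | 8.34 | 6.81 | 6.24 | 5.82 |

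Example: ICC 0.05, m = 20, n = 600, p = 0.5 gives DE = 1 + 19 × 0.05 = 1.95 and 1.96 × √(0.25 × 1.95 / 600) = 0.0559. The 600 patients are then worth 600/1.95 = 308 independent ones.

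**Step 3: the ICC at which ±5 is lost.** The largest tolerable DE is (5 / unadjusted half-width)², and the ICC limit is (DE − 1)/(m − 1).

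| n | p | Unadjusted half-width | Largest DE | ICC limit, m=10 | ICC limit, m=20 |
|---|---|---|---|---|---|
| 400 | 0.50 | 4.90 | 1.041 | 0.005 | 0.002 |
| 600 | 0.50 | 4.00 | 1.562 | 0.062 | 0.030 |
| 600 | 0.30 | 3.67 | 1.859 | 0.096 | 0.045 |
| 600 | 0.24 | 3.42 | 2.141 | 0.127 | 0.060 |

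**Step 4: 400 evaluable out of 600 enrolled.** Clusters shrink to 6.7 to 13.3 patients. At ICC 0.05, DE is 1.28 to 1.62 and the half-width at p = 0.5 is 5.55 to 6.23 points.

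**Step 5: patients needed for ±5 at p = 0.5.** 384.15 × DE at ICC 0.05 gives 558 (m = 10) to 750 (m = 20). The planned 600 lies inside that range.

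**The case against.** The strongest reply is that the plan enrols 600, not 400, and that retention is likely to be well below one half. This largely stands for overall retention. Earlier retention is quoted for all patients enrolled, so 600 is the natural denominator. At 24 to 30%, ±5 survives up to an ICC of 0.045 to 0.127, depending on p and m. The reply is weaker for urine proportions, which may lie nearer 0.5, and for any analysis confined to about 400 patients.

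Second, positive correlation is plausible but not shown, and physician discretion is bounded. Detoxification vs Maintenance sets a minimum urine criterion for taper, dose has a ceiling, supply is scheduled to week 12 and capped afterwards, and retention also depends on patients. This stands, and it is why the point is conditional and the ICC is given as a range.

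Third, a reader might infer that the reported intervals, overall and by treatment setting, will be too narrow and cover less than 95%. If clustering were ignored at ICC 0.05 and m = 20, coverage would be about 84%. The protocol does not support that inference. It names no variance method, plans descriptive summaries by site and by setting, and states no interval by setting. The method may properly sit in an analysis plan that is not shown. Only the sample-size statement is open to criticism.

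Fourth, the sentence on generalising gives physician experience as its reason, so it should not be read as a formal claim of inference to a population of physicians. The point does not depend on it.

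**Conclusion.** The point holds for the precision claim. The figure of about 400 assumes independent patients, in a section that itself places 10 to 20 patients with each physician, and the word conservative is justified only for p. At n = 400 and p = 0.5 there is almost no room: the claim fails once the ICC passes about 0.002 to 0.005.

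It would go too far to say that the study of 600 misses ±5 points. At p = 0.5 it keeps that precision up to an ICC of 0.030 (20 per physician) or 0.062 (10 per physician), and further at the retention cited. The practical effect on overall retention is therefore modest, and the study is descriptive, with no test or decision rule tied to ±5. The correction is worth making for the urine proportions and for any result that rests on about 400 patients. Its size depends on an ICC that the documents do not supply.

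**What to change.** 1. In Power and Sample Size Considerations, say that p = 0.5 is conservative with respect to the proportion only.
2. Restate the precision for 600 patients with a design effect and a stated ICC range. For example: with 10 to 20 patients per physician and an ICC of 0.01 to 0.10, the half-width at p = 0.5 is 4.2 to 6.8 points, and 4.8 to 5.6 at ICC 0.05.
3. Compute the confidence intervals for retention and the urine proportions with physician as the cluster, by a cluster-robust variance or a random physician effect.
4. If intervals are also given by treatment setting, add a small-sample correction. An even split over three settings (an assumption) would leave only about 10 to 20 physicians in each, too few to rely on an uncorrected robust variance.

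The cost is a few sentences in the sample-size and analysis sections. It needs no extra patients and no extra data. The downside is that the stated precision becomes slightly less favourable.
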